Study Title:	A Phase 2, Randomized, Double-Blind, Placebo-Controlled Study of Intravenous FDY-5301 for the Prevention and Treatment of ICU Acquired Weakness in Major Trauma Patients
Study Number:	FDY-5301-203
IND Number:	142828
EudraCT Number:	2019-003429-66
Phase:	2
Purpose:	To evaluate the efficacy, safety, and pharmacokinetics (PK) of FDY-5301 compared to placebo in major trauma ICU patients at risk of intensive care unit acquired weakness (ICUAW)
Primary Objective:	To assess the effect of FDY-5301 on muscle function and organ dysfunction in the major trauma intensive care unit (ICU) population
Secondary Objectives:	To assess the effect of FDY-5301 on other clinical outcomes in the major trauma ICU population
Coprimary Endpoints:	 Chelsea Critical Care Physical Assessment Tool (CPAx) total score at Day 10, or hospital discharge, whichever occurs first Organ dysfunction total time to recovery (TTR) until Day 28
Secondary Endpoints:	The secondary endpoints will be analyzed in the following sequence:
	 Medical Research Council Sum Score (MRC-SS) at Day 28 or hospital discharge, whichever occurs first Worst Sequential Organ Failure Assessment (SOFA) score during ICU stay

Confidential Page 4 of 64

Overall survival at Day 28 Safety will be evaluated based on occurrence of or changes **Safety Endpoints:** throughout the study in the following parameters: Adverse events (AEs), treatment-emergent adverse events (TEAEs), and serious adverse events (SAEs) Clinical laboratory assessments (hematology, clinical chemistry, and thyroid function tests) 12-lead electrocardiogram (ECG) assessments **Exploratory Endpoints:** • Overall survival at Month 3 and Month 6 from date of Time to successful ventilator extubation from time of first dose Time to hospital discharge from first hospital arrival time and time of first dose, and discharge disposition (e.g., home, home with community support, rehabilitation unit, or nursing home) Incidence of sepsis through Day 28 SOFA score and sub score components at Days 1, 3, 7, 14, 21, and Day 28 or ICU discharge, whichever occurs first • CPAx total score and sub score components at Days 1, 3, 7, 10 (sub score components only), 14, 21, and Day 28 or hospital discharge, whichever occurs first • Medical Outcomes Study Questionnaire Short Form 36v2 Health Survey (SF-36v2) and activities of daily living questionnaire (Barthel Index) at Day 28 or hospital discharge (whichever occurs first), Month 3, and Month 6 Proportion of subjects who can complete any sit-to-stand maneuver and the number of sit-to-stand maneuvers completed in 30 seconds at Days 10, 14, 21, and Day 28 or hospital discharge, whichever occurs first Individual organ dysfunction TTR until Day 28 In a subset of subjects: Blood metabolic, inflammatory, and biochemical markers of muscle damage analysis at Days 1, 3, and 7 Plasma iodide concentrations evaluated at up to 4 hours (hrs) pre- and post-dose on Days 1, 3, and 7

Confidential Page 5 of 64

Leukocyte gene expression analysis at Days 1 and 7 Percent change from baseline in the level of the 3rd lumbar (L3) vertebra Skeletal Muscle Index (SMI) and

	other muscle volume measures based on Computerized Tomography (CT) scan at Day 10	
Methodology:	Randomized subjects will be dosed as soon as possible and within 48 hours of their first hospital arrival time and will receive up to 7 daily bolus intravenous (IV) doses of FDY-5301 (1 mg/kg or 2 mg/kg) or volume-matched placebo. All subjects will be followed for 6 months.	
Number of Subjects:	Approximately 252 subjects randomized in a 1:1:1 ratio	
Inclusion Criteria:	 Age 18-75 years Major trauma defined as: a. thoracic and/or abdominal and/or pelvic injury b. necessitating admission to ICU with ventilation anticipated for at least 24 hrs c. hemorrhagic shock defined as systolic blood pressure (SBP) <90 mmHG requiring blood transfusion or base deficit of at least 6mEq/L prehospital arrival or within one hour after hospital arrival IRB/IEC-approved consent obtained within 48 hours of first hospital arrival time (i.e., in case of transfers, use time of arrival to first hospital immediately post injury) 	
Exclusion Criteria:	 Likely to die within 48 hrs from time of screening Any neurological condition that is perceived at the time of hospital admission as an immediate threat to life or incompatible with good functional recovery and where early limitation or withdrawal of therapy is being considered. For example: Computed tomography imaging showing evidence of traumatic brain injury (TBI), combined with best representative Glasgow Coma Score (GCS) Motor Score of ≤4 at approximately 24 hrs post injury Evidence of nonreversible spinal cord injury Bilateral femoral fractures Women who are pregnant or breastfeeding. Women of reproductive potential must have a negative serum pregnancy test prior to randomization. Known thyroid disease or thyroid disorder, including subjects on thyroid hormone replacement therapy at the time of randomization Known allergy to iodine Chronic renal disease requiring dialysis 	
	6. Known thyroid disease or thyroid disorder, including subjects on thyroid hormone replacement therapy at th time of randomization7. Known allergy to iodine	

Confidential Page 6 of 64

	_
Test Product, Dosage and	 10. Body weight (BW) >140 kg (or >309 lb) 11. History or presence of debilitating neurologic or other neuromuscular disease (e.g., spina bifida, amyotrophic lateral sclerosis, multiple sclerosis) at time of randomization 12. Current metastatic cancer 13. Solid organ transplant recipient 14. Evidence of pre-existing sarcopenia defined as having a pre-trauma Clinical Frailty Score (CFS) of ≥5 or based on clinical judgement (e.g. frail by appearance, cachexia, etc.) 15. Use of systemic corticosteroids, immunomodulators, or oncologic chemotherapy within 6 months of randomization (inhaled and topical steroids are allowed) 16. Use of investigational drugs or devices within 30 days of randomization 17. Any clinically significant abnormality identified prior to randomization that in the judgment of the Investigator or Sponsor would preclude safe completion of the study, or confound the anticipated benefit of FDY-5301 FDY-5301 (dose of 1 mg/kg or 2 mg/kg) will be
Mode of Administration:	administered IV by bolus injection daily for up to 7 injections.
Control Product, Dosage and Mode of Administration:	Placebo (normal saline) will be administered IV by bolus injection daily for up to 7 injections. Placebo will be volume-matched and indistinguishable from FDY-5301.
Duration of Study:	Each subject's participation will be approximately 6 months from the time of screening to study exit.
Statistical Methods:	A stratified randomization scheme will be employed in this study, with presence of pelvic or lower limb fractures as the stratification factor.
	Subjects will be stratified into two groups:
	subjects with pelvic or lower limb fractures
	 subjects without pelvic or lower limb fractures
	Safety Analyses:
	All safety measures will be summarized descriptively. AEs will be summarized by Medical Dictionary for Regulatory Activities (MedDRA) system organ class and preferred term.

Confidential Page 7 of 64

Efficacy Analyses:

For comparisons between groups, the primary analysis will be the combined FDY-5301 treated groups compared to placebo. If the difference between the means of pooled treatment group compared to the placebo group is statistically significant, a step-down procedure will be followed to test the individual FDY-5301 doses compared to placebo. The following testing order of doses will be employed:

- 1) FDY-5301 2 mg/kg versus placebo
- 2) FDY-5301 1 mg/kg versus placebo

The first primary efficacy endpoint is the CPAx total score at Day 10 (or at hospital discharge, whichever occurs first). As the primary analysis, the treatment comparison of the CPAx total score will be performed using an analysis of covariance (ANCOVA). The model will include CPAx total score at Day 10 (or at hospital discharge, whichever occurs first) as a dependent variable, treatment and stratification category (with or without presence of pelvic or lower limb fractures) as factors, and "baseline" CPAx (the first available datapoint) as a continuous covariate.

The p-values, least-squares means, standard errors, and the 2-tailed 95% confidence intervals for the treatment groups and placebo group will be presented.

The second primary efficacy endpoint, organ dysfunction total TTR until Day 28, will be estimated using Kaplan-Meier estimator and compared using log-rank test at a significance level 0.05.

Sample size determination:

Approximately 252 subjects will be randomized to receive FDY-5301 1 mg/kg, 2 mg/kg, or placebo, in a 1:1:1 ratio. This sample size was established based on a 15% drop-out rate. This sample size provides greater than 90% power to detect an improvement of 6 in the CPAx total score for pooled FDY-5301 (1 mg/kg or 2 mg/kg) compared with placebo (e.g. 36 in pooled FDY-5301 group vs. 30 in Placebo group), assuming a standard deviation of 12 (Corner 2015 and Raymond 2020).

Given the assumption that the median expected organ dysfunction recovery time is 7 days for the placebo group and the median expected organ dysfunction recovery time is 4.9 days for the pooled treatment group (Xiao 2011) (i.e. an

Confidential Page 8 of 64

expected relative risk reduction of 30% and a 2-sided log-rank test at a significance level of 0.05), the study would have approximately 70% power if at least 213 events are observed (based on no subject being censored until Day 28).

The sample size calculations were based on the coprimary endpoints achieving a p-value of <0.05 each.

For secondary endpoints, a sequential analysis will be performed. The continuous secondary efficacy endpoints of MRC-SS and worst SOFA score will be analyzed with an ANCOVA model similar to the one described for the primary endpoint of CPAx total score. The secondary endpoint of overall survival at Day 28 will be analyzed using a Kaplan-Meier approach and a log-rank test, similar to the methodology described for the primary endpoint of organ dysfunction total TTR until Day 28.

μg/kg/min	microgram per kilogram per minute
μL	microliter(s)
μmol/L	micromolar per liter
mEq/L	milliequivalents per liter
mg/dL	milligram per deciliter
mL	milliliter(s)
mmHg	millimeters of mercury
MRC	Medical Research Council
MRC-SS	Medical Research Council Sum Scores
NaI	sodium iodide
NOAEL	no-observed-adverse-effect level
PaO ₂	partial pressure of arterial oxygen
PCI	percutaneous coronary intervention
PICS	post intensive care syndrome
PK	pharmacokinetics
PP	per protocol
ROS	reactive oxygen species
RR	respiratory rate
RTS	Revised Trauma Score
S2S	sit-to-stand
SAE	serious adverse event
SAP	Statistical Analysis Plan
SBP	systolic blood pressure

Confidential Page 15 of 64

Abbreviation or Specialist Term	Explanation
SF-36v2	Short Form 36v2
SMI	skeletal muscle index
SOFA	Sequential Organ Failure Assessment
STEMI	ST-elevation myocardial infarction
SUSAR	suspected unexpected serious adverse reaction
$T_{1/2}$	terminal half-life
TBI	traumatic brain injury
TEAE	treatment-emergent adverse event
T_{max}	time when the maximal concentration is achieved
TMF	trial master file
TRISS	Trauma Related Injury Severity Score
TTR	time to recovery

Confidential Page 16 of 64

1 INTRODUCTION

1.1 Disease Setting

ICU-acquired weakness (ICUAW) is characterized by peripheral muscle weakness and wasting for which no other cause can be identified besides the acute illness or its treatment (Hermans 2015, Needham 2012, Stevens 2009, Puthucheary 2013), which has been observed to last from a few weeks to years. ICUAW may be a major part of a long-term, post-intensive care syndrome (PICS) described as physical, mental and cognitive dysfunction, which extends beyond the acute hospitalization and has a major impact on the quality of life of the growing population of ICU survivors (Needham 2012). ICUAW is associated with diminished life expectancy 12 months post-discharge (Hermans 2015).

The profound inflammation and oxidative stress that occurs during critical illness leads to early depletion of many endogenous antioxidants; for example, lower circulating concentrations of tocopherol and ascorbate in association with increased concentrations of oxidized glutathione in the plasma of critically ill patients have been documented (Friedrich 2015, Goode 1995, Marshall 2007, Bertrand 1989, Metnitz 1999, Borrelli, 1996). De-iodination of thyroid hormones to release free iodide may be a beneficial endogenous reaction to injury, however the reducing capacity of that free iodide will be exceeded by anything beyond a modest injury.

FDY-5301 is designed to provide immediate and bioavailable supra-physiological concentrations of iodide, which is a potent reducing agent. In particular, it acts to catalytically degrade hydrogen peroxide; this differs from other agents which themselves are oxidized in the reaction with peroxide. The hypothesis, supported by clinical and preclinical data, is that FDY-5301 will therefore ameliorate the systemic inflammatory response and consequent tissue damage and immune dysfunction that follow major trauma, with benefits to tissues, including muscle, that are injured downstream of the initial traumatic injury.

1.2 FDY-5301 Background

1.2.1 Product Description

The active pharmaceutical ingredient in FDY-5301 Injection is sodium iodide. FDY-5301 is formulated as an isotonic solution in single-use vials for intravenous (IV) administration. The solution has a pH between 7.0 and 9.5. The chemical formula of sodium iodide is NaI.

1.2.2 Preclinical Data

Pharmacology studies have shown that iodide catalytically disproportionates hydrogen peroxide in vitro and reduced myocardial injury in several species with experimentally induced ischemia-reperfusion models. In a hind limb ischemia-reperfusion rodent model, iodide was seen to reduce muscle damage, and reduce systemic and muscle markers of inflammation.

The studies conducted for nonclinical safety assessment of FDY-5301 include pilot and Good Laboratory Practice (GLP) 7- and 14-day IV repeat-dose toxicity studies, fertility and teratogenicity studies, pharmacokinetic studies, local tolerability studies, a series of in vitro and

Confidential Page 17 of 64

in vivo safety pharmacology, in vitro hemocompatibility, in vitro cytochrome P450 induction and inhibition, in vitro protein binding, and genotoxicity studies conducted in accordance with International Council for Harmonization (ICH) guidelines.

In rats, no signs of toxicity were observed at doses up to 74 mg/kg given daily IV for 14 days. In beagle dogs, the no-observed-adverse-effect level (NOAEL) was established at 20 mg/kg for 7 days of dosing. The observed dose-limiting toxicity (DLT) at 40 mg/kg was reversible gastrointestinal inflammation.

Safety pharmacology studies included an in vitro hERG K⁺ ion channel assay, a central nervous system (CNS) safety pharmacology study (general signs and behavior) in rats, a pulmonary safety pharmacology study in rats, and a cardiovascular safety pharmacology study in dogs. Overall, the results of these studies show that at the dosing regimen and at expected systemic exposures of FDY-5301 to be achieved in humans, no adverse effects are anticipated to occur in any of the major organ systems tested.

FDY-5301 was found not to be mutagenic in the bacterial reverse mutation assay.

Other studies with FDY-5301 show that the formulation to be used for clinical trials is not expected to cause local perivenous irritation. In addition, it does not exhibit protein binding, nor does it inhibit or induce cytochrome P450 enzymatic activity. Other nonclinical assessments confirmed that FDY-5301 is not genotoxic in in vitro and in vivo micronucleus studies, does not cause irritation at injection sites, does not cause hemolysis, and is compatible with human serum and plasma.

1.2.3 Clinical Experience

Faraday has completed recruitment into three clinical trials of FDY-5301:

- Study FDY-5301-101: A phase 1 trial evaluating the safety and pharmacokinetics (PK) of FDY-5301, which included single ascending doses in 40 healthy volunteer subjects at IV doses of 0.1, 0.3, 1.0, 3.0, 10.0 mg/kg and placebo, was conducted. No significant adverse events were detected, including biochemical measures of thyroid function, and no clinically significant effects on vital signs or electrocardiograms (ECGs) were observed.
- 2. Study FDY-5301-201: A phase 2 trial in 120 subjects with acute ST-elevation myocardial infarction (STEMI) undergoing percutaneous coronary intervention (PCI) was conducted. Subjects were randomized to receive IV doses of FDY-5301 (0.5, 1, and 2 mg/kg) or volume-matched placebo within an hour prior to myocardial reperfusion for STEMI. FDY-5301 did not provoke undesirable arrhythmias based on 14-day continuous monitoring. There was a slight excess of nonsustained ventricular tachycardias (<30 seconds) in the first 48 hours in the 2 mg/kg group. At 3 months, the data suggest the subjects on FDY-5301 had smaller infarcts measured by cardiovascular magnetic resonance and better cardiac function. The adverse event profile, biochemistry testing, including thyroid function, and other safety parameters have identified no safety issues of concern.

Confidential Page 18 of 64

3. Study FDY-5301-202: A phase 2 trial in 34 subjects undergoing unilateral total knee replacement was conducted to measure the effect of FDY-5301 at a dose of 1mg/kg on quadriceps wasting after the use of a tourniquet. The pattern of TEAEs and SAEs were consistent with those normally expected in this adult population and there appears to be no relationship between any of these events and study drug when looking at the aggregate data. No significant difference was seen between the treatment groups for any of the main efficacy parameters. Outliers in both groups lead to wide and unequal variances. The data showed that the control group had no impairment in functionality at 6 weeks compared to baseline, showed no evidence of muscle wasting, and had a minimal impairment in strength. It is conceivable that tourniquet induced ischemia reperfusion injury is not a particularly conspicuous contributor to recovery after total knee replacement.

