1.2.4 Theoretical Risks and Benefits

There is a theoretical risk of thyroid dysfunction because the active ingredient is sodium iodide. Gastrointestinal irritation and bleeding were seen at 40mg/kg per day in 7-day dosing toxicology studies in dogs. The dose at which no adverse effects were seen was at 20mg/kg per day in 7-day dosing (the intended clinical doses are 1 or 2 mg/kg per day). Faraday continues to actively assess and closely monitor these potential risks in clinical trial subjects.

Trauma patients in ICU are at high risk of developing muscle weakness and other organ failures consequent at least in part to a systemic inflammatory response. This leads to short and long-term morbidity and poor outcomes and has in part been characterized as a "post ICU syndrome." This represents a very high unmet medical need for which effective and safe interventions would be of huge benefit. Subjects randomized to FDY-5301 are anticipated to have potential benefits such as improvement in muscle wasting or other organ dysfunction consequent on serious injury. Subjects randomized to placebo are not anticipated to have any adverse effects related to the administration of intravenous sterile saline. In addition, FDY-5301 or placebo will be administrated in addition to standard of care, so no subject in FDY-5301 clinical studies will have any approved treatment withheld. Subjects randomized to FDY-5301 will have the prospect of benefit from this adjunctive experimental medication.

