1.5 Justification for Dose

The selected dosing regimen for FDY-5301 is 1 or 2 mg/kg daily for 7 days and is based on the available safety, efficacy and PK modeling data for FDY-5301.

FDY-5301 is expected to provide clinically significant exogenous reducing capacity when administered to major trauma ICU patients. The systemic inflammatory response which triggers a catabolic state occurs very early following major trauma, but is postulated to last for longer than a day, and perhaps weeks following trauma (Pedroso 2012). For this reason, and given the poor outcomes expected in the ICUAW population, 7-day dosing is proposed to provide reducing capacity for a period long enough to potentially confer clinical benefit. Daily dosing is based on the half-life of FDY-5301 in healthy volunteers of 6 to 8 hours, implying a return to baseline levels after 24 hours.

Up to 10 mg/kg IV of FDY-5301 has been given to healthy volunteers in a phase 1 study without adverse effects, and a single IV bolus dose of 2 mg/kg was well tolerated in the phase 2 AMI reperfusion study in acutely ill subjects. Specifically, thyroid function tests showed similar group means across all groups, with no suggestion of a drug effect. In a published study of healthy volunteers, cumulative doses of 14 mg/kg of sodium iodide (given as daily oral doses of 1 mg/kg for 14 days) were well tolerated. (Robison 1998).

In nonclinical safety testing, the NOAEL in a rat 14-day repeat dose GLP toxicity study was 74 mg/kg/day and the NOAEL in a GLP dog 7-day repeat dose study was 20 mg/kg/day. These data support daily dosing in subjects at the high dose in this study of 2 mg/kg for up to 7 days.

The PK profile of FDY-5301 has been well characterized in humans. Following IV administration, a rapid maximal concentration (C_{max}) occurs, followed by rapid initial clearance from plasma, a terminal half-life of 6 to 8 hours, and trough levels approaching zero at 24 hours. Exposure will be adequate for daily administration without accumulation, even in subjects with renal impairment.

Confidential Page 21 of 64

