5 STUDY SCHEDULE

The schedule of assessments for all clinical trial sites is listed in Table 1. The additional schedule of assessments for US clinical trial sites only is listed in Table 2.

All study visits will be calculated from time of first IP dose (Day 1). Month 3 and Month 6 visits will be calculated based on the calendar month (e.g., if Day 1 is February 15th, Month 3 would be May 15th and Month 6 would be August 15th).

Confidential Page 29 of 64

Table 1: Schedule of Assessments

Activity	Screening		In-Hospital										Follow Up Long Term Follow Up			
	J			Day 2ª	Day 3ª	Day 4ª	Day 5ª	Day 6ª	Day 7ª	Day 10ª	Day 14ª			Day 28 If Discharged Earlier	Month 3	Month 6
			(+/-) 24hrs of 1 st IP dose								(+/-) 1 day	(+/-) 1 day	(+/-) 1 day	(+) 2 weeks	(+/-) 1 week	(+/-) 2 weeks
Informed Consent	X											,				
Eligibility Criteria	X															
Estimated Height & Weight	X															
Medical History	X															
Demographics	X															
Physical Examination	X				X				X		X	X	X			
Serum Pregnancy Test	X															
Safety Laboratory Tests	X				X				X		X	X	X	X		
12-lead ECG		Randomization	XcXq		X				X		X		X			
TRISS		izat	X													
IP Administration		E	Χe	Χ ^f	Χ ^f	Χ ^f	Χf	Χ ^f	Χf							
CT Scan of Abdomen	Xa	pue								Xh						
SOFAi		8	X		X		à à		X		X	X	X			
Sit to Stand	26									Х	X	X	X		O.	
СРАх			X		X				X	Х	X	X	X			
MRC-SS							à à		å f				X			
Barthel Index													X		X	X
SF-36v2 Health Survey									à f				X		X	Х
Organ Dysfunction TTR			X	X	X	X	X	X	X	X	X	X	X			
Time of Extubation			X	X	X	X	X	X	X	X	X	X	X		DA .	
Occurrence of Sepsis			X	X	X	X	X	X	X	X	X	X	X			
Discharge & Disposition	2		X	X	X	X	X	X	X	X	X	X	X		X	Х
General Health Inquiry															X	X
Overall Survival	. 00		X	X	X	X	X	X	X	X	X	X	X	χj	X	X
Concomitant Medications	X		X	X	X	X	X	X	X	X	X	X	X	χj		
Adverse Events	X		X	X	X	X	X	X	X	X	X	X	X	χi		1

^aIf being discharged from hospital prior to Day 28, conduct all "Day 28 or Hospital Discharge if Earlier" assessments

ⁱConducted until ICU discharge only

^jMay be conducted by phone

Page 30 of 64

^bAssessments may be conducted up to 2 days prior to discharge if earlier than Day 28

^cUp to 12 hrs pre-dose

d Up to 4 hrs post-dose

^eAs soon as possible and within 48 hrs of FIRST hospital arrival time (i.e. immediately post injury)

f(+/-) 4 hrs using the time of day of first IP dose

^gOnly if performed as standard of care within 48 hrs of first hospital arrival and up to 24 hrs after first IP dose

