6.2.7 Safety Laboratory Tests

Clinical laboratory evaluations will be performed by each site's clinical laboratory per institutional guidelines. See Appendix 2: Clinical Laboratory Tests for a list of required analytes. Additional assessments may be performed between scheduled study visits as clinically required to diagnose and monitor AEs/SAEs.

6.2.8 12-Lead Electrocardiogram

Standard 12-lead ECGs will be performed as single recordings and read at the clinical site.

Confidential Page 36 of 64

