9.3 Laboratory Abnormalities or Other Abnormal Assessments

The following laboratory or other assessment abnormalities will be considered AEs and recorded in the subject's medical record and in the CRF:

- Any result deemed clinically significant by the Investigator and that is not part of another reported clinical diagnosis
- Any result leading to discontinuation or interruption of IP
- Any result that requires therapeutic intervention or a change in subject management

Abnormalities that do not meet one of the above conditions will not be recorded on the CRF.

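### Brief ventricular tachycardia, slightly more frequent at 2 mg/kg in an earlier single-dose study, is not systematically captured in this trial, although the dose is now repeated up to seven times

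*Combined protocol and SAP*

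**What the plan says.** **The earlier observation.** Section 1.2.3 describes a phase 2 study of 120 STEMI subjects given 0.5, 1 or 2 mg/kg or placebo. It states: "FDY-5301 did not provoke undesirable arrhythmias based on 14-day continuous monitoring". The next sentence reads: "There was a slight excess of nonsustained ventricular tachycardias (<30 seconds) in the first 48 hours in the 2 mg/kg group". No counts or rates by arm are given, and the paragraph closes by finding nothing worrying in the safety data.

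**Exposure then and now.** Section 1.5 says that "a single IV bolus dose of 2 mg/kg was well tolerated in the phase 2 AMI reperfusion study". It concludes from the clinical and nonclinical data: "These data support daily dosing in subjects at the high dose in this study of 2 mg/kg for up to 7 days".

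**Planned ECGs.** Section 6.2.8: "Standard 12-lead ECGs will be performed as single recordings and read at the clinical site". Table 1 places them on Day 1 before dosing (within 12 h) and after dosing ("Up to 4 hrs post-dose"), then on Days 3, 7, 14 and 28 or discharge. The Day 3 and Day 7 tracings have no stated relation to the dose. Days 2, 4, 5 and 6 have none.

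**CRF rule.** Section 9.3 makes an abnormal result an AE if the investigator finds it clinically significant, if it stops or interrupts study drug, or if it calls for treatment or a change in management. It then says: "Abnormalities that do not meet one of the above conditions will not be recorded on the CRF".

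**Named risks.** Section 1.2.4 opens with "There is a theoretical risk of thyroid dysfunction because the active ingredient is sodium iodide" and goes on to gastrointestinal effects. Arrhythmia is not mentioned.

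**The concern.** NSVT is the only safety imbalance between arms that the protocol reports from its human studies. It was seen because those subjects were monitored continuously for 14 days. Here the patient exposure rises from one bolus to as many as seven daily ones, while planned rhythm ascertainment falls to a few snapshots.

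Runs under 30 s that end by themselves can reach the database by two routes: a scheduled tracing that happens to coincide with a run, or an AE entry. The first is close to closed by arithmetic. The second depends on someone seeing the run on monitoring that the plan does not describe, and then on a judgement under 9.3. Section 1.2.4 does not draw that person's attention to arrhythmia.

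At stake is interpretation. Section 10.2.3 summarises AEs by group and ECGs by treatment and visit, without testing. If few runs are recorded, a flat table could mean no effect or no ascertainment, and the trial would not settle the question its own background section raises. Runs that go unrecorded may not be recoverable later.

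**Working it through.** The plan states no figure for arrhythmia detection, so there is none to reproduce.

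**Inputs from the protocol**
- Window of the earlier observation: 48 h = 172,800 s; run length under 30 s (1.2.3).
- Post-dose tracings in the first 48 h: one is certain (Day 1); two if the Day 3 tracing falls by 48 h (Table 1).
- 84 subjects per arm (10.2.7).

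**Assumptions, not in the documents**
- Tracing length L = 10 s, range to 60 s.
- Run length d = 29 s, or 5 s for short runs.
- k = 1 to 20 runs per affected subject in 48 h, random in time.

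**Coverage of the first 48 h**
- One 10 s tracing: 10 / 172,800 = 0.006%. Two: 20 / 172,800 = 0.012%.
- Two 60 s tracings: 120 / 172,800 = 0.07%.

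**Chance that an affected subject shows any run on m tracings:** P = 1 − (1 − (L + d) / 172,800)^(k·m)

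| L | d | k | m | P |
|---|---|---|---|---|
| 10 s | 5 s | 1 | 1 | 0.009% |
| 10 s | 29 s | 1 | 1 | 39 / 172,800 = 0.02% |
| 10 s | 29 s | 20 | 2 | 0.9% |
| 60 s | 29 s | 20 | 2 | 2.0% |

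**Dosing period.** Take three tracings (Day 1 post-dose, Days 3 and 7) of 10 s and one 30 s run per day. Each tracing overlaps with probability (10 + 30) / 86,400 = 0.046%, so 1 − (1 − 0.00046)^3 = 0.14% for three. With ten runs per day the figure is about 1.4%.

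**Expected yield in the 2 mg/kg arm, ECG route.** Let 5% to 40% of subjects have NSVT (assumed). Low end: 84 × 0.05 × 0.0226% = 0.001 subjects. High end: 84 × 0.40 × 2.04% = 0.7 subjects.

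**Expected yield, AE route.** Suppose runs are seen, and a fraction f = 5% to 50% of affected subjects have one that meets a 9.3 condition (assumed). Low end: 84 × 0.05 × 0.05 = 0.2. High end: 84 × 0.40 × 0.50 = 16.8. The route is open, but its yield is governed by f. A true incidence of 40% with f = 5% gives 84 × 0.40 × 0.05 = 1.7 subjects; a true incidence of 5% with f = 50% gives 84 × 0.05 × 0.50 = 2.1. An eightfold difference in incidence produces nearly the same count.

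If blinding keeps f equal across arms, the ratio between arms is preserved in expectation but the counts are thinned: at 20% incidence and f = 5%, 84 × 0.20 × 0.05 = 0.84 subjects.

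**The case against.** Several points on the other side stand.

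- **Capture is conditional, not impossible.** A reader might infer that the trial cannot record NSVT at all. The documents do not support that. Section 9.1 requires every AE the investigator observes from consent to Day 28 to be recorded, regardless of ECG visits, and 9.3 admits any result meeting one of three conditions. Whether a run seen at the bedside falls under 9.3 or directly under 9.1 is not stated. Nor do the documents show that most such runs would fail all three conditions; that would be a clinical assertion.
- **The observation is weak.** A reader might infer an established arrhythmia risk. The text calls the excess slight, gives no counts, and concerns STEMI subjects dosed shortly before reperfusion. Section 1.2.3 also reports no clinically significant ECG effect in healthy volunteers given up to 10 mg/kg. Sites are told of the observation in that section. The reassurance about arrhythmias, however, came from continuous monitoring after one dose, and neither condition carries over.
- **No cumulative risk window is shown.** One might assume that each dose opens its own 48 h risk period. Section 1.5 gives a half-life of 6 to 8 h and trough levels near zero at 24 h, so that extension is not supported. The calculations above do not use it.
- **The DSMC's view is unknown.** Section 11.1 defers safety review to a charter that is not in the documents. It cannot be said that the committee would not look at arrhythmia by dose. It can only be said that it could not review from the CRF a run that was never entered there.
- **Extra recording is not merely noise.** Blinded sites might suggest that added entries only add variability. But if FDY-5301 speeds recovery, active subjects could leave monitored care sooner and have fewer runs recorded. That is a possible bias.

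**Conclusion.** The point holds as a gap in systematic ascertainment. Scheduled ECGs are practically unable to detect runs under 30 s: about 0.02% to 2.0% per affected subject for runs near 30 s, and less for shorter runs at the same frequency and tracing length. What remains is an AE route that depends on investigator judgement and on undescribed monitoring, with an assumed yield anywhere from 0.2 to about 17 of 84 subjects. The by-dose AE and ECG tables therefore cannot reliably confirm or clear the earlier observation under repeated dosing.

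The detection figures rest on assumed tracing length, run length and run frequency; the AE figures rest on assumed incidence and recording fraction. The conclusion about ECGs survives the whole range tried. The conclusion about AEs is qualitative: the yield is unknown, not zero. Nothing here shows that the drug causes arrhythmia, and the efficacy conclusions are unaffected. It is a cheap improvement worth making.

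**What to change.** 1. **Section 9.3:** exempt ventricular tachycardia from the exclusion. Any run documented during routine monitoring in the dosing period goes on the CRF with date and time, whether or not the three conditions are met. Also record whether, and until when, the subject was on continuous monitoring. State how this fits with the AE definition in 9.1.
2. **Table 1:** apply the Day 1 post-dose window to the existing Day 3 and Day 7 ECGs. This ties them to drug exposure; it does not materially raise NSVT detection.
3. **Section 10.2.3:** tabulate ventricular arrhythmias descriptively by dose group, with monitored time as denominator, and make the table available to the DSMC.
4. **Section 1.2.4:** mention the earlier observation.

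**Cost:** additional CRF fields, a table footnote, one descriptive table and a sentence. No new procedure is added, and the recording exception applies only where routine monitoring already exists. The downsides are extra entries, variation between sites in how closely monitors are reviewed, and possible differential ascertainment if arms leave monitored care at different times. The denominator addresses the last only in part, because leaving monitored care may itself depend on treatment and on the subject's condition.
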